This is an exploratory investigation of placental lesions identification by MRI and there is not data available to provide sample size justification. The goal of this sub-project is to expand the scope of our project to asses human placenta function in on-going pregnancies. Expanding the project to include women with diagnosis of FGR as per our discussion with NICHD program officer and NICHD-HPP scientific leadership was granted to us and will allow us to develop robust preliminary data for future NIH grant application. Our plan is to conduct MRI imaging and correlate the findings with placental pathology findings. We request permission to approach 60 subjects and anticipate to study a total of 20 subjects: this will provide adequate data to define future direction of this research.

RISKS AND BENEFITS

Potential direct benefits to subjects.

Results from the MRI scans will be uploaded to the subjects' EMRs. The study PI will also share the results with the subject's primary obstetric physician and will provide appropriate counseling to the subject. The clinical investigator, [name] is a Maternal-Fetal Medicine (MFM) specialist who can explain the findings of the MRI imaging and may help to reduce the subjects' anxiety. A recommendation to increase clinical monitoring may be made by the study PI based on MRI findings.

The PI will personally discuss imaging results with the clinician who is providing direct care to subject in question. The subject's primary care clinician will be involved in the discussion with subjects regarding study MRI results and any additional recommended follow-up (e.g., added subject/fetal growth monitoring). However, it will be the provider's decision if they want to take the findings of the study into consideration to make any modifications in the patient's clinical care and monitoring.

The current standard of care for FGR cases consist of increased monitoring in the following manner: non-stress test (NST) performed 2 times per week, Doppler velocimetry performed 1 time per week, and growth ultrasound performed 1 time per month after the diagnosis of FGR until delivery. Depending on the clinical manifestations, the clinicians may decrease or increase monitoring frequency for the ultimate goal of preventing perinatal mortality and morbidity. Fetal monitoring frequency will not be increased solely based on findings from the study, but rather taking into consideration other factors regarding maternal and fetal health.

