MFM clinicians use multiple tests to determine the course of care in high-risk pregnancies. The use of study results from MRI findings would only confirm standard of care decisions and not directly influence clinical care. It is not unreasonable to connect investigational imaging method knowledge to pre-existing knowledge.

The only current method to detect placental lesions is through pathologic examination of the placenta after delivery. It has been well documented that FGR fetuses with confirmed placental lesions have worse post-natal outcomes than those whose placental lesions are not confirmed. The purpose of the proposed study is to detect placental lesions before the fetus is born in an effort to come up with a better treatment plan to improve neonatal outcomes. The MRI has the potential to indicate which fetuses, based on presence or absence of placental lesions, will have a better or worse outcome at delivery. The MRI would be one of many tests taken into consideration when determining best clinical management of patients with FGR diagnosis.

The following benefits are anticipated.

1. Potential to confirm that there are no perfusion defects and no evidence of macrophage recruitment in the placental bed. This would be enormously reassuring to the subjects, particularly the absence of perfusion defects.

2. If perfusion defects or recruitment of macrophages in the placental bed are detected, we would recommend the following modifications to their clinical care.
 - a. If fetal growth is not already being monitored, we would recommend to the clinic that additional monitoring be added to clinical care.
 - b. The number of visits for patients would be increased to monitor for development of new or acceleration of hypertension, indicative of pre-eclampsia.
 - c. Depending on the severity of placental lesions, we may inform to clinicians to which patients may require earlier delivery.

In this context, these three modifications will empower clinicians to provide individualized care based on novel advanced and sophisticated imaging information.

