[name], PhD, [name] and [name]. The MRI research team will analyze and interpret the findings of the MRI imaging to determine if macrophages are detected in the uterine wall. The study PI, [name], and [name] will make the final decision for interpretation of the MRI imaging.

The PI will provide appropriate counseling to the subject and their primary obstetrician, as he is a Maternal-Fetal Medicine (MFM) specialist who can explain the findings and to reduce the subjects' anxiety. [name] is a UW Ob/Gyn physician, working in the UPH-Meriter Perinatal Clinic who routinely reviews MRI scans and counsels patients with at-risk pregnancies. [name] is the most qualified physician-scientist in the region to explain to the subject the meaning of the findings and how she will be monitored.

The study PI will disclose results from the MRI scan to subjects. The primary finding will be the presence or absence of macrophages at the maternal-fetal interface at the site of implantation. If we observe other changes in the placenta, such as lack of perfusion in intervillous space, we will also report this finding. The PI will discuss these findings with the subject in layman's terms and describe the modifications in clinical care as a result of these findings.

Interpretation of clinical monitoring will be enhanced based on MRI findings.

We may confirm that there are no perfusion defects and no evidence of macrophage recruitment in the placental bed. This would be enormously reassuring to the subjects, particularly the absence of perfusion defects. However we will not suggest to the clinician to change the course of monitoring.

If we detect perfusion defects or recruitment of macrophages in the placental bed, we would suggest that these subjects have following modification in clinical care.

- a. If fetal growth is not already being monitored, we would recommend to the clinic that additional monitoring be added to clinical care.
- b. The number of visits for patients may be increased to monitor for development of new or acceleration of hypertension, indicative of pre-eclampsia.
- c. Depending on the severity of placental lesions, we may inform clinicians as to which patients may require earlier delivery.

In this context, these three modifications will empower clinicians to provide individualized care based on novel advanced and sophisticated imaging information.

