UW-ICTR has established a Data Monitoring Committee (DMC) to provide a key resource for UW-Madison investigators conducting clinical research. We plan to utilize the UW-ICTR DMC services to ensure appropriate measures are in place to promote subject safety, research integrity and compliance with federal regulations and local policies for individual clinical research protocols. These protocols are deemed in need of DMC review by the PI, the funding agency, the local Scientific Review Committee, or the local IRB, and for which no DMC exists. For these studies, the UW ICTR DMC is the primary data and safety advisory group for the Principal Investigator.

The DMC is supported in its mission of safety and compliance by experienced ICTR staff to provide administrative assistance, experienced members representing a diversity of backgrounds, skills and knowledge, and the use of the ICTR OnCore clinical research management system which allows more efficient tracking of protocols and protocol subjects. In providing oversight for the conduct of this study, the ICTR DMC meets annually during the length of study. Additional meetings are scheduled as determined by the DMC or as requested by the PI. The DMC members review protocol-specific reports created by statisticians that serve a non-voting member role on the DMC using data pulled from the ICTR OnCore clinical research management system. These standard reports include an overview of study objectives, a review of actual and projected accrual rates, an evaluation of patient demographics for balance of randomization, and a summary of the number and seriousness of adverse events.

An interim analysis of study results may be performed and source documents may be reviewed to allow the DMC to independently judge whether the overall integrity and conduct of the protocol remain acceptable based on data provided and reported by the Principal Investigator. The DMC will make recommendations to the Principal Investigator that could include actions of continuation, modification, suspension, or termination.

ICTR Study Monitoring Service (SMS)

While many institutions involved in clinical research conduct various types of quality assurance reviews and audits, UW ICTR is one of the few institutions to offer independent Study Monitoring Services, a robust academic equivalent to the Industry Contract Research Organization (CRO) standards for ongoing study monitoring.

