Definitely Related: An AE categorized as Definite is clearly related to the intervention. If the timing of the AE is definitely consistent with the exposure to the study intervention and it is most likely that the AE was caused by the study intervention such as because a high occurrence of the AE was expected based on the study intervention materials? In this case, the PI may categorize the AE as definitely related.

Probably Related: An AE that is likely related to the use of the drug. A Probable AE is likely related to the intervention. If the timing of the AE is consistent with the exposure to the study intervention and it is more likely that the AE was caused by the study intervention than not, the PI may categorize the AE as Probable.

Possibly Related: An AE that may be related to the use of the drug. If the timing of the AE is reasonably consistent with the exposure to the study intervention, and there is another cause of the AE that could be equally likely, the PI may categorize the AE as Possible.

Unlikely Related: An Unlikely AE is one that is doubtfully related to the intervention. The coincidence of the AE with the exposure of the investigational product or intervention should be assessed. An AE that continued while the intervention was interrupted or stopped, or if the AE resolved while the intervention continued, may be categorized as Unlikely. If there is another more likely cause of the AE, the PI may determine that the AE was unlikely related to the study intervention.

Not Related/Unrelated: An Unrelated AE is one that is clearly NOT related to the intervention. An AE may be considered Unrelated if the subject did not receive the study intervention or if there is another obvious cause of the AE (for example, a car accident or other disease/condition).

Adverse Events of Special Interest

Adverse events pertaining to the subject (mother) or neonate child occurring after the signing of consent until 6 weeks post-delivery, will be collected. Conditions that are

routinely encountered by obstetricians or pediatricians, such as C-section or infant jaundice, will be recorded on the adverse event log, but will not be reported (i.e. entered into OnCore) per clinical investigator's judgement. All adverse events meeting the HS-IRB reportable event requirements will be entered into OnCore, regardless of being considered a routine condition.

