Adverse events that are expected in pregnancy and assessed as not related/unrelated to the protocol will not be reported to the ICTR DMC and entered into OnCore. These events include but are not limited to nausea and vomiting, dizziness, abdominal discomfort, back pain, vaginal discharge, and Braxton Hicks contractions.

Given the exclusion criteria and MRI screening, we do not anticipate any major events related to the MRI procedure. However, it is possible that patients report claustrophobia or anxiety in the large bore MRI machines. This may potentially require that we reduce the BMI cutoff from 39.9 Kg/m² to a lower value for the purpose of our study examination. The adverse response and claustrophobia concerns, even in a wide bore MRI research equipment, is one of the reasons we are choosing the BMI range of 18.5-39.9 Kg/m² for our study purposes.

Any planned hospitalizations for the delivery will not be reported as an SAE, but if any AE occurs during delivery or if the hospitalization is lengthened due to safety concerns this will be reported.

Genetic conditions, birth defects, or cardiac defects not recorded or suspected prior to consent will be documented as adverse events.

Any event may be documented and followed for up to 1 year post-delivery upon investigator's discretion.

Serious Adverse Event Reporting Requirements

Adverse Events that are:	Notify HS IRB	Notify DMC	Notify FDA** (events related to Ferumoxytol-MRI only)
Serious Suspected/Related* Unexpected	Within 14 business days	Within 14 business days	Notify FDA and all participating institutions as soon as possible, but no later than 15 calendar days after learning of the event
Serious Life threatening or Fatal Suspected/Related* Unexpected	Within 1 business day (24 hours) of learning of the event.	Within 1 business day (24 hours) of learning of the event.	Within 7 calendar days of learning of the event

* The UW-Madison HSIRB requires immediate reporting of serious adverse events that are probably or definitely related, whereas the FDA requires reporting of these events that are possibly, probably or definitely related. Therefore if an event is reported to the HSIRB, the event will also be reported to the FDA.

Reporting requirements to the ICTR Data Monitoring Committee

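### The safety plan neither identifies nor attributes deliveries brought forward because of the study MRI

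*Combined protocol and SAP*

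**What the plan says.** Two parts of the protocol meet here.

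**From scan to delivery.** Potential direct benefits to subjects lists what the team would recommend if perfusion defects or macrophage recruitment are found. The third item reads: "Depending on the severity of placental lesions, we may inform to clinicians to which patients may require earlier delivery". The later text on interpreting and disclosing MRI findings repeats it: "we may inform clinicians as to which patients may require earlier delivery". The benefits section also undertakes to tell participants that the method is not an established diagnostic test. Counselling is due within two weeks of the last scan.

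**From delivery to safety report.** Adverse Events of Special Interest states "Any planned hospitalizations for the delivery will not be reported as an SAE", and the same sentence goes on: "but if any AE occurs during delivery or if the hospitalization is lengthened due to safety concerns this will be reported". That section also says that conditions obstetricians or pediatricians see routinely, "such as C-section or infant jaundice, will be recorded on the adverse event log, but will not be reported", meaning not entered in OnCore, at the clinical investigator's judgement. Events that the Health Sciences IRB requires to be reported go into OnCore even if routine. The Data Monitoring Committee section says that the committee's reports are prepared "using data pulled from the ICTR OnCore clinical research management system".

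**The concern.** The study MRI is unvalidated, and its result is returned during pregnancy with a possible message about delivery timing. If a delivery is brought forward partly because of that message, the change in timing is an effect of the study procedure. A safety plan should be able to count such deliveries and show them to the oversight committee.

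As written, the exemption is broad enough to take in an induction or caesarean scheduled after the scan, and nothing asks whether the scan played a part. The Preeclampsia and FGR Risks section lists the neonatal consequences of preterm delivery, so the question matters. At stake is whether the committee could tell a delivery driven by the underlying disease from one that the research imaging helped to bring about.

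**Working it through.** The plan gives no figure on this point, so the check is a reading of the rules side by side.

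**Timing.** Visit 2 may fall from 29 3/7 to 36 4/7 weeks. Adding up to two weeks for counselling gives at the latest 29 3/7 + 2 0/7 = 31 3/7 weeks for the earliest scan and 36 4/7 + 2 0/7 = 38 4/7 weeks for the latest. Results can therefore arrive while delivery timing is still open, in some women well before term.

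**Test case.** Take two women with the same gestational age at a scheduled delivery, the same mode of delivery and the same neonatal outcome. In one, the clinician cited the study MRI in deciding the timing; in the other, not. Which planned record differs?

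| Rule or record | MRI cited | MRI not cited |
|---|---|---|
| SAE exemption for delivery admissions | Exempt if planned; the term is not defined | Exempt if planned |
| Exception in the same sentence | Covers events during delivery or a longer stay, not the decision on timing | Same |
| Caesarean section | On the log; OnCore entry by judgement | Same |
| Obstetric data from record review | Gestational age, birth weight, neonatal outcome, maternal complications requiring preterm delivery | Same items |
| Neonatal events to 6 weeks | Collected; routine ones may stay out of OnCore | Same |
| Review of pregnancy outcome with the safety board | Outcome shown; link to the MRI not required | Outcome shown |
| Standard DMC report | Objectives, accrual, demographics, number and seriousness of events | Same |
| Study stopping guidelines | Claustrophobia or anxiety, and anaphylaxis only | Same |

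No listed item separates the two women.

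**The remaining route.** The IRB override and the attribution assessment could separate them, but only for something already treated as an adverse event. The serious-event reporting table also requires the event to be related and unexpected. Relatedness would rest on what the investigator happens to know, since no field asks. Preterm delivery is described as a raised risk in FGR, so it could readily be classed as expected.

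**Plausibility of false-positive scans, for scale only.** The documents give no specificity, so 70% to 95% is assumed. Treat the constitutionally small share as lesion-free, also an assumption.

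- With the 40% in the case-selection framework, m = 0.40 × 20 = 8. Expected false positives, m × (1 − specificity), run from 2.4 down to 0.4. The chance of at least one, 1 − specificity^m, runs from 0.94 down to 0.34.
- With the 60% diagnostic error rate in the Background, m = 12. The ranges are 3.6 to 0.6 and 0.99 to 0.46.

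These figures count scans, not deliveries brought forward, and do not measure the gap.

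**The case against.** The strongest reply is that outcomes are well covered. The exemption removes only the admission. Its own sentence keeps events during delivery and safety-related lengthening of stay reportable. Maternal and neonatal events are collected to 6 weeks after delivery, IRB-reportable events reach OnCore even if routine, and the Data and Safety Monitoring Plan has the pregnancy outcome and any effect on the fetus reviewed with the DSMB (read here as the same committee as the DMC). Reporting requirements to the ICTR Data Monitoring Committee adds that all recorded events will be available through OnCore. On care decisions, "it will be the provider's decision if they want to take the findings of the study into consideration", and MRI results "would only confirm standard of care decisions and not directly influence clinical care".

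Most of this stands. A reader might infer that harm from a misleading scan is hidden from safety review; the provisions just listed do not support that. A reader might also infer that an admission prompted by the scan is by definition planned, or that early delivery is the main harm of the study. The protocol neither defines planned nor ranks harms.

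Three things do not answer the narrower point. Seeing an outcome is not the same as recording why delivery occurred when it did. The provider's final say does not remove the study's contribution: the protocol says that monitoring frequency will not be increased on study findings alone, but gives no matching statement for delivery. And the assurance that results will not directly influence care sits beside the statement that earlier delivery may be flagged, so it cannot settle the matter. The promise that all recorded events reach OnCore likewise conflicts with the rules keeping some of them out.

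**Conclusion.** The point holds as an attribution gap. Followed as written, the plan can show the committee an early delivery and its consequences, but nothing requires the contribution of the study MRI to be recorded or shown, and the admission itself may be exempt.

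The gap applies to all 20 planned participants. How many deliveries it would affect cannot be estimated: the documents give neither the accuracy of the MRI nor how often clinicians would act on it, and the message is tied to lesion severity rather than to any positive finding. The conclusion rests on the listed data items being complete in this respect; a field in a case report form outside these documents could narrow it. It should be corrected because the protocol itself describes the path from scan to delivery timing.

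**What to change.** 1. In Adverse Events of Special Interest, limit the exemption to deliveries whose timing was decided without reference to the study MRI.
2. Add to the delivery case report form the indication for delivery and whether the MRI result contributed to its timing. Gestational age and neonatal outcome are already collected, and the coordinator already reviews the maternal and newborn records at the Delivery Visit.
3. Enter each delivery to which the MRI contributed in OnCore, with attribution to the study procedure assessed. List it with gestational age and neonatal outcome in the DMC report.
4. Reconcile the statements in the benefits section and in the text on disclosure of findings on whether MRI results influence care. Also reconcile the statement that all recorded events reach the DMC through OnCore with the rules that keep some out.

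The cost is one sentence, one or two form items and a few more entries in DMC reports. The change concerns reporting only and implies no view on when any woman should be delivered.

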Critical analysis of literature suggests that anaphylaxis may occur in 0.02 % of subjects receiving ferumoxytol, making it one of the safest intravenous iron preparation. Furthermore, the data on SAEs derived from Adverse Event Reporting System have inherent limitations of limited information on safety precautions taken prior to iron infusion and treatments rendered for suspected adverse events, since some of the treatments used for drug reactions to intravenous iron themselves have inherent risks of causing serious adverse events compounding the interpretation of these data.

Other common adverse reactions reported in Ferumoxytol-treated patients include diarrhea (4.0%), constipation (2.1%) and hypertension (1.0%).

Toxicological data in animals or prior studies in humans with ferumoxytol does not suggest additional risks of particular severity or seriousness over and above what is

described above. This is so because we plan to use substantially lower dose during gestational window well beyond the period of organogenesis.

If there is an unforeseen adverse reaction, we would use the usual and customary treatment for iron infusion-associated allergic reactions, which would be no different from response to any other allergic reaction case at the obstetric triage unit. In order to facilitate and create the utmost safety, we would pre-notify the obstetric anesthesiologist on the unit in advance of the scheduled procedure. After the patient completes intravenous iron infusion and has been monitored for at least a total of an hour and has not experienced any adverse side effects, the patient will be advised to present herself for the ferumoxytol-MRI. The coordination for this will be provided by the study coordinator assigned to the study.

The vast majority of serious allergic reactions occur within short time (10 minutes) of starting the infusion. No reactions have been reported after 30 minutes of infusion. We have arbitrarily extended observation period to one hour and no one is expected to develop allergic reactions after that time.

Patients have hemogram done routinely for clinical care at 28 weeks. We will perform a panel of iron study (serum iron and transferrin levels) two-three weeks after the day of infusion. TIBC is not useful in settings of patients having received iron infusion, hence is not included in the panel.

Supporting Documentation for Safety of Ferumoxytol use in Pregnant Women

Ferumoxytol - Pregnancy reports in AMAG safety database

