Specific Aim 1: MRI Flow

- 2D Phase Contrast MRI (Flow Imaging) = FDA approved, clinical sequence

Specific Aim 2: MR Perfusion and Oxygenation

- Oxygenation (BOLD MRI) – multi TE gradient echo sequence = FDA approved sequence

Specific Aim 3: MRI Ferumoxytol DCE perfusion data (not investigational sequences) and localization of immune cells.

DATA AND SAFETY MONITORING

Data and Safety Monitoring Plan

We use the UW ICTR Data Monitoring Committee for the purpose of oversight over this study. We have accounted for the fees for the Data Safety Monitoring. The clinical investigator, [name], the PI, [name] and the co-investigator [name], respectively, are responsible for reporting any adverse responses or events that occur. These are reported as per requirement to UW IRB, and to the Data Monitoring Committee. We take advice from the IRB committee and Data Monitoring Committee for appropriate modifications of our procedures in order to avoid such events.

For subjects receiving the ferumoxytol infusion, the PI and study team will monitor any potential impact on the subject and the fetus. The subject will be closely monitored by triage clinical staff during the infusion of ferumoxytol in the triage unit, including the collection of vital signs. With any signs of reactions, the infusion will be stopped. The study coordinator will report any events of this nature, including adverse events and unanticipated problems, to the PI and the DSMB within one business day.

In the weeks following infusion, the PI will discuss the imaging results with the subject and the clinician providing direct care to the subject. Any adverse events will be documented, entered into the subjects study file and reported to the DSMB. After delivery, pregnancy outcome and any potential impact on the fetus will be documented and reviewed with the PI and subject clinician and DSMB. Development of pre-

eaclampsia and FGR will not be considered, but will be reported, as an adverse event secondary to ferumoxytol infusion.

Data Monitoring Committee (DMC)

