All recorded AEs will also be available to the ICTR DMC by completing the AE/SAE forms in OnCore. The reporting requirements are consistent with those of the HS IRB, as well as the same timeframe. Once entered into OnCore, an automatic notification of an SAE will be sent to the ICTR DMC as an automated notification.

Study Stopping Guidelines

The study will be stopped or significantly changed if at least one of the following occurs:

- More than 10% of subjects experience severe claustrophobia or severe anxiety related to the MRI procedure
- For subjects receiving ferumoxytol, the study will be stopped or significantly changed if 2 subjects have an anaphylactic reaction

Subject Stopping Guidelines

If the subject experiences any adverse events or any issues arise that may affect the subject's safety, the subject will be withdrawn from the study.

The Principal Investigator (PI) may discontinue or withdraw a subject from the study for the following reasons at his/her discretion:

- If any clinical adverse event (AE), laboratory abnormality, or other medical condition or situation occurs such that continued participation in the study would not be in the best interest of the subject
- There is evidence of progressive disease or unacceptable toxicity

BIBLIOGRAPHY

4. Catalano P, deMouzon SH. Maternal obesity and metabolic risk to the offspring: why lifestyle interventions may have not achieved the desired outcomes. *Int J Obes (Lond)*. 2015;39(4):642-9. doi: 10.1038/ijo.2015.15. PubMed PMID: 25777180.

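### The only pre-specified, mandatory study-level action on anaphylaxis is at two cases; a first case would be hard to reconcile with the stated 0.02% rate, yet nothing in the available text holds the next infusion until it is reviewed

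*Combined protocol and SAP*

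**What the plan says.** Study Stopping Guidelines: "the study will be stopped or significantly changed if 2 subjects have an anaphylactic reaction". This is the only event count for anaphylaxis in the text available to me.

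The section on allergic and anaphylactic reactions states that "anaphylaxis may occur in 0.02 % of subjects receiving ferumoxytol". It gives no numerator, denominator or interval. The sample size is 20, each woman receives a single 255 mg infusion, and the Replacement of Subjects section allows up to 2 replacements.

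Several things follow a first reaction:

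- **The affected woman.** "With any signs of reactions, the infusion will be stopped" (Data and Safety Monitoring Plan). Under the Subject Stopping Guidelines, if her safety may be affected, "the subject will be withdrawn from the study". The obstetric anesthesiologist has been alerted beforehand, and she is observed for an hour (Supportive Care).
- **Notification.** The coordinator reports such events, "including adverse events and unanticipated problems, to the PI and the DSMB within one business day". Entering a serious event in OnCore also sends an automatic notice to the DMC. Serious, related and unexpected events go to the IRB, DMC and FDA on set deadlines.
- **Possible study-level response.** "We take advice from the IRB committee and Data Monitoring Committee for appropriate modifications of our procedures in order to avoid such events" (Data and Safety Monitoring Plan). The DMC section says that "the ICTR DMC meets annually during the length of study", adds that "Additional meetings are scheduled as determined by the DMC or as requested by the PI", and lets the committee recommend continuation, modification, suspension or termination.

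**The concern.** These steps stop one infusion, remove one woman from the study, inform people, or permit a decision. None says that the next woman must wait until the first case has been reviewed. Whether she waits depends on the investigator's or the committee's discretion, or on where the annual meeting falls.

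That matters because one case in so small a study would be a strong signal against the risk on which the protocol relies. The subjects are pregnant, and the protocol concedes that data on ferumoxytol in pregnancy are limited. The infusion is a research procedure and iron deficiency is not an entry criterion, so holding it postpones no clinically indicated treatment. A review after a first case is also the natural point to re-check screening, dose and infusion rate before anyone else is exposed.

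**Working it through.** **Inputs.** Rate p = 0.02% = 0.0002 (allergic/anaphylactic reaction section). n = 20 (Sample Size), or 22 if both replacements are also infused. Trigger r = 2 (Study Stopping Guidelines). The plan states no operating characteristics for the rule and no counts behind 0.02%, so there is no figure of its own to reproduce.

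**1. How likely is a case at the stated rate?** Exact binomial:

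- At least one in 20: 1 − 0.9998^20 = 0.00399, or 0.40%. For n = 22 it is 0.44%.
- At least two in 20: 1 − 0.9998^20 − 20 × 0.0002 × 0.9998^19 = 7.6 × 10⁻⁶, or 0.0008%.

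The plan's trigger is an event roughly 500 times less likely, at the stated rate, than the first case (0.00399 / 0.0000076 ≈ 525).

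**2. What would a first case say about the rate?** If it occurs in the nth woman infused, the exact two-sided 95% lower limit is 1 − 0.975^(1/n).

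| First case at woman | Lower limit | Multiple of 0.02% |
|---|---|---|
| 1 | 2.5% | 125 |
| 5 | 0.51% | 25 |
| 10 | 0.25% | 12.6 |
| 20 | 0.13% | 6.3 |

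The limit is above 0.02% at every position. For one case in all 20 (5%), the full interval is 0.13% to 24.9%.

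**3. How often would each trigger fire if the true rate were higher?** The rates below the first row are assumptions; n = 20.

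| True rate | At least 1 case | At least 2 cases |
|---|---|---|
| 0.02% | 0.40% | 0.0008% |
| 1% | 18.2% | 1.7% |
| 2% | 33.2% | 6.0% |
| 5% | 64.2% | 26.4% |
| 10% | 87.8% | 60.8% |

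At a true 5% the two-case rule would not fire in 1 − 0.264 = 74% of studies; at 10% it would not fire in 39%.

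**4. How many women could be infused after a first case?** These are worst cases: they assume that nobody pauses infusions or calls a meeting before the next annual one. If exactly one case falls at random among 20 and all 20 are infused between two meetings, the mean is (20 − 1)/2 = 9.5; with 22 infused it is (22 − 1)/2 = 10.5. The documents give no accrual rate. Assuming even accrual of 20 over T years with a meeting at each year-end, the mean is (20/T − 1)/2, which is 4.5 for T = 2 and 2.0 for T = 4.

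Averaged over all studies at the stated rate, the expected number infused after a first case is the sum over k = 1 to 20 of p(1 − p)^(k−1)(20 − k) ≈ 0.0002 × 190 = 0.038.

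**The case against.** A reader might infer that nothing can happen at study level until a second case. The documents do not support that. Advice from the IRB and DMC on changing procedures is tied to no event count, and neither is an extra DMC meeting or a recommendation to suspend. With the one-business-day report and the automatic notice of serious events, the committee should learn of a first case quickly. The expedited-reporting table covers only unexpected events, and whether anaphylaxis counts as unexpected is arguable because it is a described risk; the other two routes do not depend on that label. What stands is narrower: all these routes permit action, and none requires it before the next infusion.

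A reader might also infer that one case would contradict the 0.02% figure. That is too strong. The protocol says only that anaphylaxis may occur at that rate, gives no precision for it and notes limits in the spontaneous reports. An event with a 0.4% chance is strong evidence of a higher rate, not proof.

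It is also fair to say that one event reviewed at discretion and two requiring action is a defensible scheme for a rare, known risk managed in hospital triage. At the stated rate the hold would almost never be used. That limits the expected benefit, but it limits the cost equally: the hold operates only when a case has cast doubt on the stated rate.

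**Conclusion.** The point holds: in the available text, the only pre-specified, mandatory study-level action on anaphylaxis is at two subjects. A first case has a 0.40% chance at the stated rate, and its exact 95% lower limit, 0.13% to 2.5%, exceeds that rate wherever it falls. No available provision makes the next infusion wait for a review.

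This is a recommended, inexpensive improvement to subject safety. It does not show that the plan is in error or that the committee would fail to act. The counts of 9.5, 4.5 and 2.0 women should not be read as forecasts of unreviewed infusions, because they assume that no one uses the discretion the plan provides. If 0.02% is right, the practical effect is very small (0.038 women expected); the hold matters if the true rate is higher, which is what a first case would suggest.

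The calculations assume independent subjects with a common risk. The finding of absence is limited to the text I had: part of the protocol around the supporting safety documentation, the DMC charter and the IND application were not available, and any of them could contain such a requirement. Confidence is medium for that reason.

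**What to change.** Add one sentence to the Study Stopping Guidelines: after the first anaphylactic reaction, no further subject is infused until an unscheduled DMC review has recommended continuation, modification or suspension. Keep two cases as the outer limit. If the DMC charter already requires such a review, cite it there instead.

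This uses powers the DMC section already gives the committee, and may need a matching line in the charter. The cost is a short pause, with a 0.4% chance of being used over the study at the stated rate. Because infusion is due within 1–2 weeks of the FGR diagnosis (Visit 1) and a woman who misses a visit window is withdrawn from study treatment (Early Termination and Withdrawal), a pause could cost a waiting woman her place. A prompt ad hoc review would keep that risk small.
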